2.1 Study documents and general considerations

This document describes the procedures and conventions to be used in the final analyses with data of all patients who were included into study EP00-402.

The study is based on the

- study protocol V 1.0, dated 16 Mar 2007,
- Amendment no. 01, dated 12 Mar 2012 incorporated into protocol v 1.0 leading to protocol v 2.0, dated 12 Mar 2012,
- Amendment no. 02, dated 9 May 2012 incorporated into protocol v2.0 leading to protocol v3.0, dated 9 May 2012,
- Amendment no. 03, dated 6 Jun 2013 incorporated into protocol v3.0 leading to protocol v 4.0, dated 6 Jun 2013,
- Amendment no. 04, dated 14 July 2014 incorporated into protocol v4.0 leading to protocol v5.0, dated 14 July 2014.

This study was terminated by the sponsor [REDACTED] Following decision of [REDACTED] study termination all patients were called in for a last visit (documented on the final visit page of the case report form (CRF)).

Raw data listings, summary tables, graphs and statistical tests will be generated by means of the program SAS 9.3 or higher.

The following descriptive statistical parameters will be shown in summary tables

- Continuous variables: n (valid cases), n (missing data), mean, median, standard deviation (SD), min, max, quartiles
- Categorical variables: Count and percentage of category. Percentages are routinely based on the total category count excluding the missing category if not otherwise mentioned. Percentages showing a rate relative to the total number of patients in this group are given in special tables (e.g. Adverse Event (AE) tables). Footnotes will specify the percent basis.

For continuous variables, if not otherwise specified, mean, median and quartiles will be reported to one decimal place greater than the precision of data as collected. Standard deviation will be

presented in two decimal place greater than the data and minimum/ maximum values will be reported with the same precision, as they were collected. This rule is only valid if values are not converted for the summary.

Generally, percentages will be displayed in the format xx.d, i.e. one decimal place will be shown; if the calculated percentage is 100, no decimal is required (i.e. 100% and not 100.0%). If the count is zero no percentage needs to be shown.

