2.2 Study objectives

The primary objective of this study is to evaluate the long-term effect of growth hormone treatment on the development of diabetes in short children born SGA for 10 years after the end of treatment.

The secondary objectives of this study are:

- to report the incidence of anti-rhGH antibodies 6 months after termination of growth hormone treatment
- evaluate final height in follow-up period
- to evaluate IGF-I and IGFBP-3 levels for 10 years after end of growth hormone treatment
- to evaluate incidence and severity of adverse events

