2.3.2 Secondary Endpoints

2.3.2.1 Safety endpoints

Criteria for assessing long term safety of GH treatment focusing on the secondary objectives are:

- **Immunogenicity:** Number and percentage of patients developing anti-rhGH antibodies through the follow-up period after end of GH treatment is the secondary safety endpoint associated with monitoring and assessing immunogenicity.

Patients will be screened for anti-rhGH antibodies at baseline and 6 months after the end of treatment. Only in case of positive antibodies measurements in previous visit follow-up measurements are planned after 1 year, 5 years and 10 years. Positive antibodies are defined as values above 1.76. Unscheduled visits will be excluded from the analysis.

- **Laboratory evaluations – safety parameters:** Change from baseline (Shift from baseline, as applicable) at 6 months, 1 year, 5 years and 10 years after end of GH treatment in laboratory safety parameters as follows:
 - **Hematology:** Hemoglobin, hematocrit, white blood cell count (WBC, total and differential), red blood cell count (RBC), platelet count, mean cell volume (MCV), mean cell hemoglobin (MCH), mean cell hemoglobin concentration (MCHC), erythrocyte sedimentation rate (ESR).
 - **Biochemistry:** Creatinine, urea, aspartate aminotransferase (AST), alanine aminotransferase (ALT), gamma-glutamyltransferase (gamma-GT), alkaline phosphatase, total bilirubin, albumin, total protein, HDL, LDL, sodium, potassium, chloride, uric acid, fasting total cholesterol, fasting triglycerides, calcium, phosphorus.
 - **Thyroid function:** Free thyroxine and thyroid stimulating hormone.
 - **Urinalysis:** pH, glucose, ketones, bilirubin, protein.

- Number and percentage of patients with Adverse Events and Serious Adverse Events
- Change from baseline in vital signs parameters (blood pressure, pulse rate) and body weight, BMI, and BMI SDS will be assessed at each visit (baseline, 6 months, 1, 5, and 10 years after termination of treatment). BMI is calculated by [weight in kg] divided by [height in m]². For further details on the calculation of BMI SDS, see Section 5.1.
- Number and percentage of patients with significant finding in any body systems: head (external), eyes, ears, nose and throat, lungs, cardiovascular system, abdomen, musculo-skeletal system, skin, lymph nodes, central nervous system, and where appropriate, others. Physical examinations are performed at baseline, 6 months, 1 year, 5 and 10 years after end of treatment.

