4.7 Analysis of secondary endpoints

4.7.1 Safety evaluations

4.7.1.1 Immunogenicity

The number and percentage of patients with positive anti-rhGH antibodies (ABs) will be tabulated by visit. For patients with positive anti-rhGH results, all results of anti-rhGH testing will be listed by center, patient number, and visit and will include: parameter, value, unit (if available), and assessment if positive or negative

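### After month 6 antibody testing is planned only for previous positives, so the by-visit percentages in SAP 4.7.1.1 mix a rate in all screened patients with persistence among positives

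*SAP*

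**What the plan says.** Section 2.3.2.1 sets two testing regimes. First: "Patients will be screened for anti-rhGH antibodies at baseline and 6 months after the end of treatment". Then: "Only in case of positive antibodies measurements in previous visit follow-up measurements are planned after 1 year, 5 years and 10 years". The same section leaves unscheduled visits out of the analysis.

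The analysis in section 4.7.1.1 is a single table: "The number and percentage of patients with positive anti-rhGH antibodies (ABs) will be tabulated by visit". It adds a listing of all antibody results for patients with a positive result. It sets no percentage base and does not limit the table to particular visits.

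The general rule in section 2.1 is: "Percentages are routinely based on the total category count excluding the missing category if not otherwise mentioned". The same section allows another base in some tables ("Percentages showing a rate relative to the total number of patients in this group are given in special tables (e.g. Adverse Event (AE) tables") and adds: "Footnotes will specify the percent basis". Section 4.8 does not impute missing safety values. Section 4.1 defines the by-visit columns as month 6, year 1, year 5 and the last CRF visit, shown as EOS.

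The objective in section 2.2 is "to report the incidence of anti-rhGH antibodies 6 months after termination of growth hormone treatment". The endpoint in section 2.3.2.1 is wider: "Number and percentage of patients developing anti-rhGH antibodies through the follow-up period after end of GH treatment".

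**The concern.** From year 1 onwards, being tested depends on the outcome being measured. A by-visit percentage over available results therefore changes meaning between columns. At baseline and month 6 it is the share positive among everyone screened. At year 1 and year 5 it is the share still positive among patients already known to be positive. Set side by side, these columns can be read as a time course of immunogenicity after growth hormone is stopped, which they are not.

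A related mismatch concerns the endpoint. A patient negative at month 6 has no further planned test at year 1 or year 5, so antibodies that first appear after month 6 cannot be seen in that patient under the stated schedule. The endpoint nevertheless speaks of the whole follow-up period, while the objective speaks of month 6.

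The SAP's introduction names immunogenicity as one of two particular safety interests of the study. The analysis is purely descriptive, so the printed percentage is the result, and no later modelling step would correct it.

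**Working it through.** The SAP gives no antibody rate and no sample size, so there is no figure of its own to reproduce. The check is denominator arithmetic.

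**Inputs**
- Tested at month 6: all patients, N (2.3.2.1).
- Due for testing at year 1: month-6 positives only (2.3.2.1).
- Percentage base: non-missing results, by default (2.1). Untested patients stay missing (4.8).
- p = share positive at month 6, and s = share of those still positive at year 1. Both are assumed. Every patient due for a test is taken to have one.

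**Formulas**
- Month 6 percentage: N·p / N = p.
- Year 1 percentage over non-missing results: N·p·s / (N·p) = s.
- Known positives at year 1 as a share of those screened at month 6: N·p·s / N = p·s.
- Ratio of the last two: s / (p·s) = 1/p.

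**Results over a range of assumptions**

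| p (month 6) | year 1 over non-missing, for s = 25% / 50% / 75% | known positive among all screened | factor 1/p |
|---|---|---|---|
| 2% | 25% / 50% / 75% | 0.5% / 1.0% / 1.5% | 50 |
| 5% | 25% / 50% / 75% | 1.25% / 2.5% / 3.75% | 20 |
| 10% | 25% / 50% / 75% | 2.5% / 5.0% / 7.5% | 10 |

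The year 1 percentage does not depend on p at all. Whenever s exceeds p, the column rises from month 6 to year 1, although under this rule the number of known positives can only stay the same or fall.

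**Boundary cases.** If p = 0, nobody is due for a test at year 1 and there is nothing to distort. If s = 0, the column shows 0%.

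The share p·s is a lower bound on the true proportion positive, because new positives among untested month-6 negatives are not seen. Using the safety population as the base would therefore not give a valid rate either: it would count untested patients as negative.

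**The case against.** The strongest reply is that the percentage base is inferred. Section 4.7.1.1 does not state it, the default in 2.1 is only routine, and the exception for special tables is open-ended, with adverse event tables given as an example. Immunogenicity is a safety endpoint, and section 2.6 makes the safety population the basis of safety analyses. This stands in part: a reader might infer that the plan expressly prescribes non-missing results, and it does not. But the default applies unless something else is mentioned, and nothing else is. Section 4.7.1.3 sets the safety population as denominator for adverse events explicitly; 4.7.1.1 does not. The alternative base has its own fault, as shown above.

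Second, there are safeguards: footnotes on the base, counts beside percentages, and a listing of results for positive patients. These let a careful reader reconstruct what happened. They disclose the base but do not make columns with different selection comparable.

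Third, EOS. A reader might infer that the EOS percentage is selected in the same way. The documents do not establish this. Section 2.1 reports that the study was ended early and every patient was asked to attend a closing visit, and section 4.1 presents that CRF visit as EOS. The SAP does not say whether antibodies were measured in everyone then. This objection stands, and the point on EOS is conditional.

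Fourth, not retesting negatives is a schedule decision that belongs to the protocol, which is not at hand. That is accepted. The point concerns how the SAP tabulates and describes data collected under a rule that it states itself.

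**Conclusion.** The point holds for year 1 and year 5, and for EOS only if testing at the termination visit was not extended to all patients. Under the SAP's default base, those percentages are persistence among prior positives, larger than the known-positive share by 1/p at year 1: 50, 20 or 10 times for assumed p of 2%, 5% or 10%. The size rests on assumed values, because the SAP gives none.

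Three stronger readings are not supported:
- The table need not show a steep rise. That requires patients positive at month 6 who remain positive in a share above p.
- The stated immunogenicity objective is not compromised. It concerns month 6, when all patients are due for testing.
- The endpoint need not be cut back to month 6. It is enough to state what can and cannot be observed and to reconcile the two wordings.

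This is a secondary, descriptive endpoint, so the correction should be made but does not touch the primary analysis.

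**What to change.** In section 4.7.1.1:
- Give percent positive only at visits where all patients were due for testing: baseline, month 6, and EOS only if all patients were tested there. State which applies to EOS.
- For the other visits, report the number still positive divided by the number positive at the previous visit and tested. Label this as persistence, and show the number tested and the number not tested by design.

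In section 2.3.2.1, state that antibodies first appearing after month 6 cannot be observed in patients negative at month 6 under the planned schedule, with EOS qualified if everyone was tested then. Reconcile the follow-up-period wording of the endpoint with the month-6 objective in 2.2.

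The cost is SAP wording and one changed table shell, with no new data. If the endpoint wording comes from the protocol, the reconciliation can be an explanatory statement in the SAP and need not redefine the endpoint.

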4.7.1.2 Safety parameters - Laboratory evaluations

Change from baseline (Shift from baseline) in hematology, biochemistry, thyroid function, and urinalysis parameters will be displayed by visit using descriptive statistics and/ or frequency tables depending on the type of variable (continuous or discrete).

4.7.1.3 (Serious) Adverse events

AEs are coded according to Novartis MedDRA, Version 19.1 or higher.

Only adverse event starting or worsening during study EP00-402 will be presented. Adverse events with missing or incomplete start dates not clearly attributable as starting/worsening prior to study EP00-402 will be included in the analysis.

A general summary table of AEs will contain the total number of AEs, the total number of SAEs, and separate descriptions of the splits for the variables relationship to study drug, action taken, outcome and intensity.

The incidence of an AE is defined as the number of patients who experience that event, divided by the number of patients in the SAF population. With AE incidence, each event will be counted only once for a given patient. More specifically, if a patient reports the same event more than

once, as determined by preferred term and system organ class, that patient will be counted only once for the incidence of the AE. For example, when a patient reported three instances of headache, this patient counts only once towards the total incidence of headache. Incidence of events within a system organ class is defined similarly. Whenever incidence is cross-tabulated with intensity in the summary tables, the incidence of an AE will be calculated for each level of intensity, i.e., the number of patients who experience that AE on a certain level of intensity.

The occurrence of an AE is defined as the total number of times the event occurs in the SAF population. With AE occurrence, a patient may contribute more than once to the total occurrence count. More specifically, if a patient reports a particular event, as determined by preferred term and system organ class (and having removed duplicate reporting of the same event) more than once, each event will count once towards the total event occurrence. Using the above example, headache would be counted three times for the patient who reported three separate occurrences of headache.

Occurrence tables will provide information about rates of AEs per patient-year, calculated as $12 \times \{(\text{number of events}) / (\text{months of study exposure})\}$.

The incidence and occurrence of each AE will be reported by MedDRA system organ class and preferred term, cross-tabulated with the intensity, action taken, and outcome. Additionally, total incidence and occurrence will be provided for each system organ class.

The whole set of AE summary tables will be produced for all AEs and separately for adverse drug reactions (ADR), serious AEs and serious ADRs. Adverse events will be considered as adverse drug reactions if a causal relationship to the study drug is suspected by the investigator.

All AE data will be listed, sorted by site code, patient number, and MedDRA preferred term. This list will include: adverse event, MedDRA system organ class, MedDRA preferred term, start and stop date/day, intensity, outcome, relationship to study drug, actions taken, and a variable indicating whether an AE was considered a serious adverse event (SAE). Further, a variable identifying if an AE started or worsened on or after baseline is provided.

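### Adverse event incidence by intensity counts a patient at every level experienced, so worst-grade mild and moderate cannot be read off; a row for patients with any event should also be stated (minor)

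*SAP*

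**What the plan says.** Section 2.2 lists as a secondary objective "to evaluate incidence and severity of adverse events". Section 2.3.2.1 turns this into a patient-level endpoint: "Number and percentage of patients with Adverse Events and Serious Adverse Events".

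Section 4.7.1.3 then sets the counting rules:

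- **Incidence** of an event is "defined as the number of patients who experience that event, divided by the number of patients in the SAF population". A patient with repeated episodes is counted once: "With AE incidence, each event will be counted only once for a given patient". In the SAP's example of three headaches, "this patient counts only once towards the total incidence of headache". Organ-class incidence follows the same principle.
- **Incidence by intensity** is recalculated at each level, each cell being "the number of patients who experience that AE on a certain level of intensity". No rule assigns a patient to the highest intensity.
- **Occurrence** counts every episode.
- **General summary:** "A general summary table of AEs will contain the total number of AEs, the total number of SAEs", with splits by relationship, action taken, outcome and intensity.
- **Totals:** "Additionally, total incidence and occurrence will be provided for each system organ class". The whole set is repeated for adverse drug reactions, serious events and serious reactions.

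**The concern.** Readers of a severity table usually take each patient to sit in one column, that of the worst grade. Under the rule in 4.7.1.3, a patient with one mild and one severe headache is in both columns. The mild column then mixes patients who had only mild episodes with patients who also had worse ones, and the columns can add up to more than the row total. At organ-class level, two different preferred terms of different intensity are enough to cause this. For an objective that names severity, how many patients had mild or moderate as their worst grade is a natural question, and the planned incidence tables do not answer it.

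A second, smaller gap is that the endpoint is patients with any adverse event and with any serious one. The described outputs are event totals and patient counts by preferred term and organ class. No described table states the patient count across all organ classes.

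**Working it through.** The SAP gives no adverse event rate or sample size on this point, so there is no figure to reproduce. It also does not list the intensity levels in this section; mild, moderate and severe are assumed below. All data and probabilities are invented to show how the rules behave and are not estimates for this study.

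**1. The counting rules on a small example.** Take 10 patients in the safety population, 3 of them with events, 7 events in all:

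- Patient 1: headache mild, moderate and severe; vomiting mild.
- Patient 2: headache mild; vomiting moderate.
- Patient 3: vomiting mild.

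| Headache, patients | Mild | Moderate | Severe | Sum of cells |
|---|---|---|---|---|
| SAP rule (every level experienced) | 2 | 1 | 1 | 4 |
| Highest intensity only | 1 | 0 | 1 | 2 |

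The headache total is 2 patients under either rule. The severe cell is 1 under either rule, because a patient with any severe episode has severe as the worst grade. Only the lower cells change.

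**2. Can worst grade be recovered from the SAP's cells?** Patients with at least one moderate or severe episode number between max(1, 1) = 1 and min(2, 1 + 1) = 2. Worst-grade mild is the total minus this, so between 2 − 2 = 0 and 2 − 1 = 1. Worst-grade moderate is this number minus the severe cell, so also between 0 and 1. The cells do not settle either count.

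**3. How large could the overlap be for a patient with repeated episodes?** Assume that each episode is mild, moderate or severe with probability 0.6, 0.3 or 0.1, independently. With k episodes, the chance of filling a given cell is 1 − (1 − p)^k.

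- k = 2: 0.84 + 0.51 + 0.19 = 1.54 cells per patient.
- k = 3: 0.936 + 0.657 + 0.271 = 1.864 cells per patient.
- k = 3, mild: shown in the mild cell 1 − 0.4³ = 93.6%; mild as worst grade 0.6³ = 21.6%.
- k = 3, moderate: shown 65.7%; worst grade 0.9³ − 0.6³ = 0.729 − 0.216 = 51.3%.
- k = 3, severe: shown 27.1%; worst grade 1 − 0.9³ = 27.1%, the same.

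These figures apply only to patients with repeated episodes. If a patient's episodes all have the same intensity, one cell is filled and the overlap is zero.

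**4. Patients with any event.** In the example, the described tables give 7 events and organ-class totals of 2 (nervous system) and 3 (gastrointestinal), which sum to 5. The endpoint is 3 of 10 (30%). Organ-class totals overlap, so in general they only bound it: invented organ-class rates of 30, 25, 20 and 15% are compatible with anything from 30% (the largest) to 30 + 25 + 20 + 15 = 90% (the sum).

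**The case against.** The strongest defence is that the intensity rule is explicit, unambiguous and programmable. The SAP nowhere says that the cells represent worst grade or add up to the total, and a footnote that they are not mutually exclusive would prevent misreading. That stands as a lighter remedy, but a footnote still leaves the worst-grade mild and moderate counts unavailable.

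Four stronger readings are tempting, and the document does not support them:

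- **That the two counting rules contradict each other.** The once-per-patient rule governs the total incidence of a preferred term or organ class. The intensity cells have their own definition. The totals are not double-counted.
- **That worst-grade severity is not shown at all.** The highest-intensity cell already equals the worst-grade count for that level, per preferred term and per organ class.
- **That the same rule is laid down for action taken and outcome.** The per-level rule is stated for intensity only. Those cross-tabulations are planned without a counting rule of their own, and where to display them is a matter of layout.
- **That the patient-level endpoint is undefined or lost.** Section 2.3.2.1 fixes the numerator and section 4.7.1.3 the denominator. Section 2.1 says that adverse event tables show rates relative to all patients in the group. The planned listing, with patient number, serious flag and on-or-after-baseline flag, yields the count. What is missing is only an explicit summary row, and nothing in the SAP excludes one.

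**Conclusion.** The point holds as a minor improvement. The any-level rule lets the mild and moderate cells include patients whose worst episode was more severe, and the cells need not sum to the preferred-term or organ-class incidence. No planned count is wrong under its own definition.

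The size in this study is unknown. It depends on how often one patient has events of differing intensity within a preferred term or organ class, and the SAP gives no data on that. The illustrative contrast of 93.6% against 21.6% rests entirely on assumed probabilities, independence and three episodes per patient.

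The row for patients with any event is an alignment of the described tables with a stated endpoint. The primary diabetes endpoint and the event rates per patient-year are unaffected.

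**What to change.** In section 4.7.1.3, replace the rule for incidence by intensity with wording such as: *In incidence tables by intensity, each patient is counted once per preferred term, once per system organ class and once overall, at the highest intensity recorded. All episodes at all intensities are shown in the occurrence tables.*

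Add to the incidence tables for all adverse events, serious events, adverse drug reactions and serious reactions a first row, *patients with at least one event*, with n and % of the safety population.

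The cost is a change of SAP wording and a small change to the table programs. The downside is that the number of patients who also had a milder episode would be available only from the listing, since occurrence tables count events, not patients. No change is proposed for action taken or outcome.
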